5.0 STUDY DESIGN

This is a prospective single-center clinical trial in which a maximum of 187 eyes will be consented, enrolled, and treated with the VisuMax™ femtosecond laser.

Study subjects will be followed for 12 months. Subjects will be screened for eligibility, and informed consent will be obtained from those who meet screening criteria and are interested in participating in the study. Eligible subjects will be examined preoperatively to obtain a medical history and to establish a baseline ocular condition. Baseline and postoperative measurements will include manifest refraction, cycloplegic refraction, distance visual acuity (best corrected and uncorrected using ETDRS charts), slit-lamp examination, fundus examination, corneal topography and wavefront, corneal tomography (front and back corneal surface), central corneal pachymetry, dynamic pupillometry (dark, scotopic, and mesopic), whole-eye wavefront analysis, mesopic contrast sensitivity, and intraocular pressure (IOP).

All baseline and postoperative measurements will be done in accordance to the daily routine procedure of the clinic for standard SMILE treatments.

Retreatments of the study eye will not be allowed during the course of the study.

6.0 STUDY POPULATION

6.1 INCLUSION CRITERIA

6.1.1 General inclusion criteria

Only patients who are medically suitable for corneal refractive surgery can be included in the study.

As general inclusion criteria the following aspects are defined:

- Subjects should be 21 years of age or older
- Contact lens wearers must stop wearing their contact lenses at least four weeks per decade of wear before baseline measurements in case of hard contact lenses and one week before baseline measurements in case of soft contact lenses.

6.1.2 Inclusion criteria specific to the protocol

- Eyes with high myopia spherical equivalent between -9.00 D up to -14.00 D, with cylinder up to 7.00 D will be included.

| | | |
|------------|-------------|----------------------------|
| 01/02/2016 | Version 3.0 | CONFIDENTIAL Page 12/28 |
|------------|-------------|----------------------------|

- Calculated sub-lenticule thickness (SLT) $\geq 220 \mu\text{m}$
- Calculated total uncut stromal thickness (TUST) $\geq 300 \mu\text{m}$
- The corrected distance visual acuity will be 20/40 or better in each eye pre-operatively.
- Patient will be able to understand the patient information and willing to sign an informed consent.
- Patient will be willing to comply with all follow-up visits and the respective examinations as specified in the flow-chart.

6.2 EXCLUSION CRITERIA

6.2.1 General exclusion criteria

- Previous intraocular or corneal surgery of any kind on the eye being treated
- Patient not being able to lie flat in a horizontal position
- Patient not being able to tolerate local or topical anesthesia
- Autoimmune diseases
- Sicca syndrome, dry eye
- Herpes viral (herpes simplex) infections
- Herpes zoster
- Diabetes
- Pregnant or nursing women (or who are planning pregnancy during the study)
- Patients with a weight of $> 135 \text{ kg}$
- Any residual, recurrent or acute ocular disease or abnormality of the eye, e.g.
 - Cataract
 - Suspected glaucoma
 - Corneal disease
 - Corneal thinning disorder, e.g. keratoconus,
 - Pellucid marginal corneal degeneration
 - Dystrophy of the basal membrane
 - Corneal oedema
 - Exudative macular degeneration
 - Infection
- Any residual, recurrent, or active abnormality of the cornea to be treated, e.g.
 - Existing corneal implant
 - Corneal lesion

| | | |
|------------|-------------|--------------|
| 01/02/2016 | Version 3.0 | CONFIDENTIAL |
| | | Page 13/28 |

- Unstable refraction
- Connective tissue disease
- Dry eye

The complete list of contraindications is included in the Surgical Information Package provided to the patient by the London Vision Clinic before surgery. Furthermore, the contraindications related to a SMILE treatment correspond to those reported in the medical literature for laser refractive surgery.

| | | |
|------------|-------------|----------------------------|
| 01/02/2016 | Version 3.0 | CONFIDENTIAL Page 14/28 |
|------------|-------------|----------------------------|

7.0 STUDY PROCEDURES

7.1 PRE-OPERATIVE ASSESSMENT

Note: As soon as the first screening for each patient is done and the patient is enrolled in the study, patient data will be pseudonymized. Only the investigator and monitor will be able to identify the patient name if necessary.

Informed consent and permission to use data for analysis and publication have to be obtained from each patient prior to the pre-operative assessment.

A full ophthalmologic examination will be performed on all patients prior to surgery as described in the schedule of assessments (chapter 8.2).

7.2 OPERATIVE PROCEDURES

The treatment protocol will provide information as described in the schedule of assessments and as usually done in daily practice for SMILE.

Schedule of Assessments

| Examination | preOP | OP | 1d | 1m | 3m | 12m |
|---|-----------|----|--------|----------|-----------|------------|
| Days to treatment | -60 to -1 | | 1 to 2 | 21 to 42 | 75 to 110 | 305 to 440 |
| Patient Demographics, medical history | X | | | | | |
| Informed consent | X | | | | | |
| Pupil diameter (Procyon) | X | | | | | |
| Intraocular pressure (IOP) (Goldmann) | X | | | | | X |
| Fundus examination | X | | | | | X |
| Cycloplegic refraction | X | | | | | |
| Subjective refraction | X | | X | X | X | X |
| Contrast sensitivity | X | | | | X | X |
| Slitlamp examination | X | X | X | X | X | X |
| Corneal topography and wavefront (ATLAS) | X | | X | X | X | X |
| Corneal tomography (Pentacam) | X | | | | X | X |
| Wavefront (WASCA) | X | | | | X | X |
| Optical quality (HD Analyzer) | X | | | | X | X |
| Corneal & epithelial thickness (RTVue OCT) | X | | | | X | X |
| Ocular Response Analyzer | X | | | | | X |
| Severe side effects / complications | | X | X | X | X | X |
| UDVA | X | | X | X | X | X |
| CDVA | X | | | X | X | X |
| Patient questionnaire for night vision disturbances | X | | | | X | X |
| Light Disturbance Analysis (LDA) | X | | | | X | X |
| Treatment protocol and videos | | X | | | | |
| Laser settings | | X | | | | |

Note: All described examinations are usually done in daily routine practice.

| | | |
|------------|-------------|--------------|
| 01/02/2016 | Version 3.0 | CONFIDENTIAL |
| | | Page 15/28 |

8.0 AVERSE EVENT REPORTING

DEFINTION OF AN ADVERSE EVENT (AE)

An AE is any unfavourable and unintended sign (including an abnormal laboratory finding), symptom or disease temporally associated with the use of a medical treatment or procedure that may or may not be considered related to the medical treatment or procedure.

REPORTING OF AES

Patients will be instructed by the investigator to report the occurrence of any AE. The investigator assesses and records all AEs observed during the AE reporting period which is defined as postoperative until the end of the study. Any event considered as related to the procedure will be reported regardless of timing.

DEFINITION OF SERIOUS ADVERSE EVENT (SAE) SAES DURING STUDY PERIOD

A SAE includes any of the events listed in Table 1 below and occurring between registration and until completion of the study.

| | | |
|------------|-------------|----------------------------|
| 01/02/2016 | Version 3.0 | CONFIDENTIAL Page 16/28 |
|------------|-------------|----------------------------|

Table 1 SAE Definitions

| | Comments |
|---|--|
| Fatal | All events resulting in death |
| Life-threatening | The patient was at immediate risk of death from the event as it occurred. It does not include an event that, had it occurred in a more serious form, might have caused death |
| Requires inpatient hospitalization (> 24 hours) | Events not considered to be SAE are hospitalizations > 24 hours and occurring under the following circumstances: - elective surgery (planned before entry into the trial) - part of the normal treatment or monitoring of the trial treatment - hospitalization for social reasons (e.g. in rehabilitation home) - progressive disease |
| Prolongs hospitalization | Prolongation of an existing hospitalization |
| Disabling | Includes persistent or relevant disability or incapacity |
| Secondary malignancy | Any new malignancy other than a relapse of the current tumour |
| Congenital anomaly | Birth defect of offspring |
| Other medically significant condition | Important AEs that are not immediately life-threatening or do not result in death or hospitalization but may jeopardize the patient or may require intervention to prevent one of the other outcomes listed above |

SAEs after End of Trial Treatment

During the follow-up phase, the following events have to be reported as SAE:

- fatal, life-threatening and other medically significant events possibly, probably or definitely related to late effects of trial treatment
- disabling events possibly, probably or definitely related to late effects of trial treatment
- secondary malignancy
- congenital anomaly

DEFINITION OF SERIOUS ADVERSE DRUG REACTIONS (SADRS)

SADRs are all SAEs considered to be related (possibly, probably, definitely) to the trial treatment.

RECORDING OF SAEs

Any SAE must be recorded by completion of an SAE form within 24 hours of becoming aware of the SAE.

REPORTING OF SAEs TO THE REGULATORY AUTHORITIES

The London Vision Clinic will report all SAEs to the regulatory authorities as required by local and national guidelines.

An overview of expected adverse events and serious adverse events is shown in appendix 1.

8.1 SURGICAL COMPLICATIONS

If any surgical complication occurs, the surgeon will finish the treatment of the patient as usually done in daily routine practice for SMILE. This patient might be excluded from the efficacy analysis if the surgical problem can be defined as a reason for low predictability or loss of lines of CDVA. However, the patient will be still included in the safety investigation and will be reported in the intermediate and final report. If necessary, single patients will be described in detail as case reports.

An overview of intraoperative surgical complications, is shown in appendix 1.

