3.0 STUDY OBJECTIVES

The primary objective of this study is to evaluate the safety and efficacy of the Carl Zeiss Meditec VisuMax™ femtosecond laser SMILE procedure for the reduction or elimination of myopia with spherical equivalent from -9.00 D to -14.00 D with a maximum cylinder of 7.00 D (high myopia with or without astigmatism). The secondary objective of the study is to establish appropriate safety parameters for SMILE surgery given that they have been set to be the same as LASIK.

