4.0 STUDY ENDPOINTS

4.1 MAIN ENDPOINT

1. Standard deviation of $SE_{postop} - SE_{target}$ at each follow-up time point (represent the scatter of the refractive outcome)
2. Difference in keratometry between the 3 months and 12 months' time points to be the same as for group of matched LASIK eyes.

| | | |
|------------|-------------|----------------------------|
| 01/02/2016 | Version 3.0 | CONFIDENTIAL Page 10/28 |
|------------|-------------|----------------------------|

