4.2 SECONDARY ENDPOINTS

The secondary, descriptive endpoints will include:

3. Cumulative UDVA distribution at each time point compared to pre-operative CDVA (efficacy diagram A⁵⁴).
4. Distribution of lines difference between post-operative UDVA and pre-operative CDVA in order to normalize the improvement in visual acuity between eyes (efficacy diagram B⁵⁴).
5. Change in CDVA as a loss-of-line distribution at each time point (safety diagram C⁵⁴) including the percentage of eyes with CDVA unchanged or lines gained, and the percentage of eyes with a loss of 2 or more lines.
6. Cumulative distribution of CDVA at each time point.
7. Stability of spherical equivalent refraction (SE) (diagram F⁵⁴):
The mean and standard deviation at each time point will be calculated, as well as the percentage of eyes with a change of 0.5 D and 1.0 D between 1-month- and 3-months follow-up, and between 3-months and 12-months follow-up.
8. Predictability of spherical equivalent including linear regression analysis of achieved SE depending on attempted SE (diagram D⁵⁴).
9. Spherical equivalent refractive accuracy (diagram E⁵⁴):
Distribution of $SE_{postop} - SE_{target}$ at each follow-up time point.
10. Refractive astigmatism as a distribution of pre- and post-operative astigmatism at each follow-up time point (diagram G⁵⁴).
11. Side effects and complications at each time point (numbers and percentages) according appendix 1.
12. Standard analysis of corneal aberrations with focus on spherical aberration with ATLAS pre- versus post-operative and stability of corneal aberrations post-operative for all follow-up visits with an ATLAS.
13. Cylinder vector analysis according to the Alpins method⁵⁵ including predictability of the target induced astigmatism vector relative to the surgically induced astigmatism vector, and the distribution of the angle of error (angle between the target induced astigmatism vector and surgically induced astigmatism vector) (diagrams H and I⁵⁴).

| | | |
|------------|-------------|--------------|
| 01/02/2016 | Version 3.0 | CONFIDENTIAL |
| | | Page 11/28 |

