9.2 DETERMINATION OF SAMPLE SIZE

The main criterion for the study is to evaluate the standard deviation of the $SE_{\text{postop}} - SE_{\text{target}}$, which represents the scatter of the refractive outcome. This metric was chosen in place of the predictability of the refractive correction as a mean under or overcorrection can be adjusted for simply using a nomogram, so the scatter is an indicator of the best possible refractive predictability.

To calculate the sample size for this study, the standard deviation of the refractive outcome will be compared to that reported for LASIK for an equivalent range of myopia. In a previous study of 480 eyes using the MEL80 excimer laser for myopia between -8.00 and -14.00 D, we found the standard deviation of the spherical equivalent refraction 1 year after LASIK to be 0.70 D.⁵⁶ A one-tailed F-test will be used to test if the variances of the two populations are equal, or that the variance of SMILE is not greater than the variance of LASIK, using a difference of 0.15 D in standard deviation.

Null hypothesis: $\text{Variance(LASIK)} = \text{Variance(SMILE)}$

Test hypothesis: $\text{Variance(LASIK)} < \text{Variance(SMILE)}$

Given standard deviations of 0.70 and 0.85 D, the ratio of variances is 1.47. Using an α error probability of 0.05 and a statistical power (1- β error probability) of 0.8, the a priori sample size calculation indicates that a population size of 168 eyes is required.

The 1 year follow-up rate for routine refractive surgery patients at London Vision Clinic has been >90%, so it is reasonable to expect this level of follow-up would be achieved for the study population. Therefore, a total population of 187 eyes is required.

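### Section 8.1 allows complicated patients with poor results to be left out of the efficacy analysis; on its natural reading this reaches main endpoint 1 and tends to lower the SMILE standard deviation

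*Combined protocol and SAP*

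**What the plan says.** Section 8.1 of the combined protocol and SAP provides that a patient with a surgical complication "might be excluded from the efficacy analysis if the surgical problem can be defined as a reason for low predictability or loss of lines" (CDVA lines). It adds: "However, the patient will be still included in the safety investigation and will be reported in the intermediate and final report". It does not say who decides, when, on what threshold, or whether the refractive result is known at that time.

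Main endpoint 1 in Section 4.1 is the SD of postoperative minus target spherical equivalent (SE), "at each follow-up time point (represent the scatter of the refractive outcome". Section 9.2 compares it with LASIK by a one-tailed F-test, to show that the variances are equal or that "the variance of SMILE is not greater than the variance of LASIK". The LASIK SD of 0.70 D comes from earlier work: "In a previous study of 480 eyes using the MEL80 excimer laser for myopia between -8.00 and -14.00 D".

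The efficacy analysis is not defined. Section 9.1 refers to standard reporting graphs and names no analysis set, and Section 9.2 adds none.

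**The concern.** The rule needs an actual complication, so it does not permit trimming of outliers in general. Among complicated patients, however, exclusion is a matter of choice, and the criterion is a poor postoperative result. Deciding which eyes enter a measure of spread partly by how far they missed the target acts directly on that measure.

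The direction matters because the favourable finding in Section 9.2 is that SMILE does not scatter more than LASIK. Removing eyes with large errors shrinks the SMILE SD and makes that finding easier to reach.

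Excluded patients remain visible in the safety results and the reports, but that does not put their errors back into the SD or the F-test. The wording also works by patient while the analysis counts eyes, so an uncomplicated fellow eye could be removed too.

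**Working it through.** **Does the rule reach main endpoint 1?** The documents do not settle this.
- For the narrow reading: in Section 4.2 only endpoints 3 and 4 carry the efficacy label, the first being "Cumulative UDVA distribution at each time point compared to pre-operative CDVA (efficacy diagram A". Section 9.2 also says of the SD: "This metric was chosen in place of the predictability of the refractive correction".
- For the broad reading: Section 3.0 states "The primary objective of this study is to evaluate the safety and efficacy of the Carl Zeiss Meditec" device's SMILE procedure, and refractive scatter belongs to efficacy, not safety. The trigger in Section 8.1 is low predictability, and Section 9.2 goes on to treat the scatter as an indicator of the best achievable predictability. A predictability trigger would make little sense if only the UDVA graphs were meant.

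The broad reading is the natural one, but it is an inference.

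**Inputs from Section 9.2.** SDs 0.70 D (LASIK) and 0.85 D (SMILE), one-tailed alpha 0.05, power 0.80, 168 evaluable eyes, 187 in total, 480 LASIK eyes in the reference study.

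**The plan's own figures.** The variance ratio is R = (0.85/0.70)² = 1.4745. With equal groups, power = P(F(n−1, n−1) > F₀.₉₅/R). Power of 80% needs n = 166 per group with R = 1.4745, or 169 with R rounded to 1.47, so 168 is reproduced. 168/0.90 = 186.7, rounded up to 187. With all eyes kept, power for 168 SMILE eyes is 0.805 against 168 reference eyes and 0.921 against 480.

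**Where the test turns.** With an observed LASIK SD of 0.70 D, the F-test rejects when the SMILE SD exceeds 0.70 × √1.2908 = 0.795 D (168 reference eyes) or 0.70 × √1.2255 = 0.775 D (480).

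**Removing one eye.** If 168 eyes have SD 0.85 D and one eye lies e from the mean, the new SD is √[(167 × 0.85² − e² × 168/167)/166].
- e = 0: 0.853 D
- e = 2 D: 0.838 D
- e = 3 D: 0.820 D
- No change at e = 0.85 × √(167/168) = 0.847 D

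An eye removed for CDVA loss with an accurate SE therefore raises the SD slightly. Only errors beyond about 0.85 D lower it.

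**Chance of detecting the excess scatter.** The documents give no complication rate and no error SD for complicated eyes, so these are assumed. I simulated 100,000 trials per case, with 168 SMILE eyes and overall SD 0.85 D. Each eye is complicated with probability p. Complicated eyes have error SD s, and the SD of the others is set so that the overall value holds. Complicated eyes with absolute error above 1 D (also assumed) are dropped, either all of them or each with probability one half because exclusion is optional. The F-test is then run against a simulated LASIK variance.

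| p | s (D) | LASIK eyes | All kept | All qualifying dropped | Half dropped |
|---|---|---|---|---|---|
| 1–3% | 0.85 (unrelated to complication) | 480 | 92% | 90–92% | not run |
| 1–3% | 1.0–1.25 | 480 | 92% | 85–91% | not run |
| 1% | 1.5–2.0 | 480 | 90–92% | 85–89% | not run |
| 2% | 1.5 | 480 | 91% | 84% | 88% |
| 2% | 2.0 | 480 | 88% | 73% | 82% |
| 2% | 1.5 | 168 | 80% | 70% | 75% |
| 2% | 2.0 | 168 | 77% | 58% | 69% |

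Differences of about one percentage point should not be given weight. At p = 2%, 168 × 0.02 = 3.36 eyes are complicated on average. The expected number dropped is 1.70 (s = 1.5) or 2.07 (s = 2.0), and the mean SD after exclusion is 0.828 or 0.807 D.

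**Is it only the smaller n?** No. Removing 3 to 8 eyes unrelated to outcome leaves power at about 0.80 (168 reference eyes) or 0.91–0.92 (480). The loss comes from the link to outcome.

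**The case against.** Four points deserve weight.

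1. **The trigger can be read another way.** It may mean a type of complication known to degrade accuracy, whatever the result in that eye. That reading would remove the selection on outcome. The choice would still be optional, and Section 8.1 gives no list of types. It refers to Appendix 1 for intraoperative complications, but the Appendix 1 text available lists adverse events without such a heading.
2. **Leaving out technical failures may be a legitimate target.** Section 9.2 is interested in the best achievable predictability. In the 2% cases the uncomplicated eyes have SD √[(0.85² − 0.02s²)/0.98] = 0.83 D (s = 1.5) or 0.81 D (s = 2.0), close to the SDs after exclusion. Much of the lost detection is thus a change of population. This stands as a case for a secondary analysis. Section 3.0, however, evaluates the procedure, of which complications are part. Complicated eyes with good results would also stay in, so the remaining set is not a clean uncomplicated group.
3. **The size depends on assumptions.** This stands. The largest falls need 2% complications, an error SD of 2.0 D and every qualifying eye dropped. The simulation also leaves out accurate eyes excluded for CDVA loss, which would raise the SD slightly.
4. **The LASIK reference may also exclude complicated eyes.** The documents do not say. If it does, exclusion could be the matched comparison; if not, exclusion on the SMILE side alone is unfair. A like-for-like comparison cannot be confirmed either way.

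**Conclusion.** The concern holds and should be fixed, with moderate confidence. Section 8.1 contains an optional exclusion tied to a poor result, and nothing in Section 9 offsets it. That it applies to main endpoint 1 is the natural reading but not an explicit statement. For complicated eyes with large errors, the bias is toward finding SMILE no more variable than LASIK.

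The size is unknown. Against 480 reference eyes and with all qualifying eyes dropped, the assumed cases run from almost no loss of detection to a fall from 88% to 73%. Against 168 reference eyes the worst case is 77% to 58%. The upper ends are illustrations, not forecasts.

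**What to change.** Replace the exclusion sentence in Section 8.1 with wording such as:

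> All treated eyes with the relevant measurement at a given follow-up time point (for main endpoint 1, a refraction) are included in the main and all efficacy analyses at that time point, whatever surgical complications occurred.

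In addition:
- State in advance whether a treated eye includes one whose lenticule was not removed, and list such eyes individually either way. This choice is influential. If one unfinished eye has an error of 9 D (assumed), the SD of 168 eyes becomes √[(166 × 0.85² + 81 × 167/168)/167] = 1.10 D instead of 0.85 D.
- Label any analysis without complicated eyes as a sensitivity analysis. Carry it out by eye, with complication types listed in advance and applied regardless of outcome.
- State whether the LASIK SD of 0.70 D was computed with or without complicated eyes. If without, show the matching sensitivity analysis beside the main result.

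The cost is one sentence, one definition, one statement about the reference and, if the sensitivity analysis is wanted, a short list of complication types. No extra eyes, visits or measurements are needed, and 168 and 187 stand. The reported SD may be slightly larger.
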